No pharmacological dilation will be used in this study. Subjects will be in a dark room aiming to achieve a natural pupil diameter of at least 5 mm. Upon inclusion, if a subject cannot achieve a non-dilated pupil diameter of at least 5 mm, they will be excluded from the study. If a subject meets a 5 mm pupil on most time points/lenses, but not all, inclusion of data acquired smaller than 5 mm will be scaled to 5 mm and considered on an individual basis.

Equipment:

1. An aberrometer (e.g. COAS-HD or CSO Osiris) will be used for all optical measures. The aberration data will be obtained for central 3- and 5-mm diameter areas. Wavefront data will be reconstructed by both modal (up to 6th order Zernike polynomials) and zonal (local slope) methods.
2. A Medmont corneal topographer will be used following each set of aberration measures to also monitor the tear film upon the eye/contact lens.

SUBJECTSSample Size:

This section describes the rationale and approach used to establish the minimum sample size (N) needed to achieve 80% power at a nominal significance level $\alpha=0.05$ for detecting a mean difference between percentage change in RMS of higher-order wavefront aberrations measured over a 12-hr period for the test lenses and the percentage change observed without a contact lens (no-CL). For each subject and lens, a series of five RMS measurements will be obtained at 0 hours (baseline) and at six, 2-hr intervals within each period. Technically, the statistical power for testing the contact lens main effect will depend not only on the structure of the covariance matrix but also on how the baseline measurements recorded at time=0 hours are incorporated into the statistical model(s). But, given the degree of uncertainty about the input parameter values required to estimate sample size, we believe it reasonable to base initial calculations on a dependent sample t-test on a mean difference score under the assumption of no differential carryover effect. Thus, the target parameter of interest for our primary analysis corresponds to the true difference in the mean post-baseline percentage change over 12 hours between each of the test contact lenses and no-CL for N subjects. Note that this test would be equivalent to testing the interaction of "lens" and "hours of use" factors in a two-way repeated measurements ANOVA.

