Data was not available on the two test lenses, so we used previously published data on an ALCON lens expected to provide similar responses. Specifically, we approximated parameter values for [1] effect size, [2] within-subject variance, and [3] within-subject correlation from the data reported in two previous studies. Specifically, Montes-Mico, *et al* (2013) measured wavefront aberrations in 15 myopic eyes before and at 2-hr intervals after contact lens fitting over a 12-hr period. Using the 5-mm pupil diameter data presented in Figure 2 of the referenced paper, we estimated that the group-averaged percentage change between the baseline (i.e., 2-hr after lens fitting) and the final measurement (i.e., after 12-hr wearing time) of ~3% and ~5% for no-CL and DAILIES TOTAL ONE (DT1) lens, respectively. Note that this difference between no-CL and DT1 was smaller than any of the other lenses under test, but mirrors the expectation for the current test lenses. To allow for mean differences larger than the observed 2% mean difference between each of the test lenses and no-CL in the current study, we added a 1.5% non-inferiority margin; thus, our sample size calculation assumes a 'null difference' of 3.5%.

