The primary outcome measure in this study will be a derived variable indexing the percentage change in the RMS of higher-order wavefront aberrations (microns) at a 3 and 5 mm pupil from baseline to 12 hours. For each participant, we will convert the data from microns into the percentage change in RMS, $\% \Delta_{i(12-0)k} = 100 \times (\text{RMS}_{i12k} - \text{RMS}_{i0k}) / \text{RMS}_{i0k}$ where $i=1,2,\dots,N$ participant, j represents time (hrs) $\in (0 \text{ (BL)}, 2, \dots, 12)$, and k denotes lens. Our initial analysis will compare the mean $\% \Delta_{(12-0)\text{test}}$ computed across N participants for each of the Air Optix plus Hydraglyde and Air Optix Aqua lenses independently with the mean $\% \Delta_{(12-0)\text{NCL}}$ with no contact lens.

Secondary:

1. *Subject-reported vision-stability (0-100 scale, while viewing at distance)*
2. *Root Mean Square Fit Error.* For each optical measurement, the wavefront will be reconstructed using both a 'typical' modal (Zernike) reconstruction and zonal (local integration) reconstruction. The difference between these two reconstructed wavefronts will be evaluated.

TESTING PROCEDURES:

In office testing will be done at study entry, and following 2 ± 1 days of lens wear for each of the follow up visits.

Testing Day 1, Visit 1 Baseline/Inclusion:

1. Demographics
2. Ocular history
3. Entrance Snellen visual acuity
4. Entrance ocular health (with conjunctival and corneal staining)
5. Habitual lens information (type, power)
6. Habitual lens use (wearing schedule, replacement schedule, hours per day, insertion time, removal time)
7. Subjective refraction (best objective with an additional -0.25 D for subjective improvement)
8. Fit evaluation of all lens pairs. If all lens pairs do not fit adequately enough per investigator clinical determination for dispensing, subject will be exited from the study.
9. Snellen acuity of each eye for all lens pairs.

Testing Day 2, Visit 1-7 Naked eye diurnal measures:

1. Subjects will first have aberrometry, Medmont topography, and subjective quality measurements acquired every 2 ± 0.5 hours for 12 ± 1 hours without any lenses (no lens, baseline). The subject will wear their habitual spectacles between measurement periods.

Testing Day 3, Visit 1-7 and Testing Day 4, Visit 1-7 (each separated by a day of washout and 2 ± 1 days of study lens wear):

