where μ is the overall mean, α_i is the effect for the i^{th} sequence, $\rho_{j(i)}$ is the random effect for the j^{th} individual within the i^{th} sequence (i.e. $\rho_{j(i)} \sim N(0, \sigma_\rho^2)$), γ_k is the effect of the k^{th} period, τ_l is the effect of the l^{th} lens effect and λ_m is the effect of the m^{th} carryover effect with e_{ijkl} being the NIID residual term (i.e., $e_{ijkl} \sim N(0, \sigma_e^2)$). Assuming that there is no statistical evidence of a period x lens interaction ($\gamma\tau_{kl}$), we will use a one-sided equivalence (i.e., non-inferiority) test to determine whether the average percentage increase in higher-order RMS induced by Dailies1 Lens is no worse than the average increase without a contact lens. In practice we can use a single directional paired-sample t-test to test the null hypotheses. If we reject H_0 we should conclude that the percentage increase over a 12-hour period in higher-order RMS induced by each of the test lenses is no worse than the increase measured without a contact lens. In this context, smaller differences in the mean difference in higher-order RMS are “better.” Thus, the statistical hypotheses are arranged so that rejecting the null hypothesis for the specified null difference implies that, the observed mean change over 12 hours for each of the test lenses is not significantly worse than the mean change with no-CL. i.e.,

$$H_0: \mu_D - \mu_{NC} \geq M_{IN} \text{ versus } H_a: \mu_D - \mu_{NC} < M_{IN}$$

Interpretation of non-inferiority test of the Dallies Total1 (test) to the reference non-contact lens (active control). Shaded area represents the non-inferiority range. Hypotheses are arranged so that larger mean difference values lead to rejection of the null hypothesis. ■ = observed point estimate of mean difference; both A and C show 1-sided confidence intervals; B and D show 2-sided CIs. Both A and E imply that Dallies Total1 is non-inferior to active non-contact lens control because the entire CI is below non-inferiority margin (3.25%). C and D imply the Dallies is inferior although a larger sample is needed to shrink the CI so that the entire interval C falls in the region of inferiority.

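### The primary outcome is set at both 3 mm and 5 mm, so each lens has two primary results and no rule says which decides or whether both must pass.

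*Combined protocol and SAP*

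**What the plan says.** The document is the combined protocol and SAP.

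- **Outcome Measures, Primary.** The outcome is taken "at a 3 and 5 mm pupil from baseline to 12 hours". The formula that follows is indexed by participant, time and lens, with no index for pupil diameter. The initial analysis compares the mean change with the no-lens mean "for each of the Air Optix plus Hydraglyde and Air Optix Aqua lenses independently".
- **Equipment** (synopsis and main text). "The aberration data will be obtained for central 3- and 5-mm diameter areas", without ranking the two.
- **Statistical Analysis.** "we can use a single directional paired-sample t-test to test the null hypotheses". No diameter is attached to the test, and no rule covers two results for one lens.
- **Subjects, Sample Size.** The expected changes of about 3% (no lens) and 5% (comparison lens) were obtained "Using the 5-mm pupil diameter data presented in Figure 2 of the referenced paper". To the resulting 2% difference "we added a 1.5% non-inferiority margin; thus, our sample size calculation assumes a 'null difference' of 3.5"%. No diameter is given for the added 1.5%, the SD of 2.1% or the correlation.
- **Synopsis, Hypothesis.** The two lens-versus-naked-eye statements are listed as separate hypotheses 1 and 2.

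**The concern.** A participant has two values of the primary variable for each lens, one per diameter, and both bear on the same hypothesis. Two analysts could follow the text faithfully and reach different primary conclusions, one from 3 mm and the other from 5 mm. The plan would not say who was right.

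What is at stake depends on the rule eventually adopted. If success at either diameter is enough, each lens has two chances at 0.05 and the error rate exceeds the nominal level. If success at both is needed, the error rate is protected, but the power stated for one test no longer applies. If one diameter decides, N=21 stands as calculated, but the plan must say which one before the results are seen.

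**Working it through.** **Inputs** (Sample Size section and Table 1): null difference 3.5%, SD 2.1%, correlation 0.80, alpha 0.05. N=21 appears in Table 1(b) only at a mean difference of 2.75% with correlation 0.80 (stated power 0.803), so I take that as the design row. The figure legend under Statistical Analysis gives a margin of 3.25% instead. That is a separate inconsistency, and I use 3.5% because the table does.

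**Step 1: reproduce the plan's figure.**
- SD of the paired difference: 2.1 × √(2 × (1 − 0.80)) = 1.328.
- Non-centrality: √21 × (2.75 − 3.5) / 1.328 = −2.59.
- Power is the probability that a non-central t on 20 df falls below the lower 5% point of the central t. It is 0.803, as stated.

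The same one-sided 0.05 calculation reproduces all 15 rows of Table 1(b). A two-sided 0.05 test does not: at N=21 its power is 0.692, and it would need 27 pairs. The sample size therefore spends the full one-sided 0.05 on a single test per lens.

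**Step 2: two diameters for one lens.** The documents give neither a correlation between the 3 mm and 5 mm differences nor any 3 mm input. I assume correlations from 0 to 0.9 and apply the same mean difference, SD and margin at 3 mm. The results come from 200,000 simulated trials of N=21 per setting, with normally distributed differences.

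The false-claim column puts the true difference at 3.5% for both diameters. The power columns put it at 2.75% for both.

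| Assumed correlation | False claim if either suffices | Power, at least one passes | Power, both pass | Diameters disagree |
|---|---|---|---|---|
| 0 | 9.7% | 0.961 | 0.64 | 32% |
| 0.5 | 8.8% | 0.917 | 0.69 | 23% |
| 0.9 | 6.7% | 0.855 | 0.75 | 10% |

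Checks and derivations:
- False claim at correlation 0: 1 − 0.95² = 0.0975, in line with the simulation.
- Both pass at correlation 0: 0.803² = 0.6448.
- Both pass otherwise: 2 × 0.803 minus the probability that at least one passes. This gives 1.606 − 0.917 = 0.689 and 1.606 − 0.855 = 0.751.
- Disagreement: at least one minus both, which is 0.961 − 0.645 = 0.316, 0.917 − 0.689 = 0.228 and 0.855 − 0.751 = 0.104.

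**Step 3: one diameter named.** The calculation returns to Step 1: N=21 and power 0.803 for each lens, on the plan's own inputs.

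**The case against.** The best defence is that 5 mm is plainly the working diameter. Subjects must have a mesopic pupil above 5 mm, the analysis diameter is at least 5 mm, data from smaller pupils are scaled to 5 mm, and the expected effect is read from 5 mm data. This makes 5 mm the natural choice, but these are measurement requirements and planning inputs. They do not override an outcome definition that names both diameters.

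A second defence is that the two results will be strongly related, since the 3 mm zone is the centre of the 5 mm zone in the same eye. That is likely, and it makes the independence figures (9.75% and 0.64) the unfavourable end of the range. At a correlation of 0.9 the excess error is under 2 percentage points and the power loss about 5 points. The power loss also depends on the 2.75% row. At a true difference of 2%, N=21 has power 0.998 even at one-sided 0.025, so requiring both would cost almost nothing if 3 mm behaved like 5 mm.

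A reader might infer three stronger things that the documents do not support:
- *Four primary tests with a familywise error of 1 − 0.95⁴ = 18.5%.* This adds the two lenses to the two diameters. The lenses answer separately stated hypotheses and are compared separately, so adjustment across them is debatable. Naming one diameter would leave that question where it is. The gap here is two diameters per lens.
- *The whole sample size and margin rest on 5 mm.* Only the 3% and 5% changes, and so the 2% part of the null difference, are tied to 5 mm.
- *A deliberate option to choose the better result.* The text is silent on the rule; it does not announce a choice after the fact.

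**Conclusion.** The point stands as a missing decision rule within each lens hypothesis. Followed as written, the plan gives two primary results per lens and a sample size for one.

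Over assumed between-diameter correlations of 0 to 0.9, with the 5 mm inputs carried over to 3 mm:
- the false non-inferiority rate per lens is about 9.7% down to 6.7% if either diameter may carry the claim, given a true difference at the margin for both;
- power per lens is about 0.64 up to 0.75 if both must pass, at the 2.75% difference behind N=21;
- under that same difference the two diameters give conflicting answers in about 32% down to 10% of trials.

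The correlation range and the carry-over to 3 mm are my assumptions. Actual 3 mm power is unknown because the plan gives no 3 mm effect, SD or margin. The conclusion that a rule is missing depends on neither assumption.

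**What to change.** In Outcome Measures, Primary, state that the single primary outcome for each lens is the percentage change in higher-order RMS at 5 mm from time 0 to 12 hours. Move the same measure at 3 mm to the secondary outcomes as a supportive result, and name 5 mm where the paired t-test is specified in Statistical Analysis. The two lens hypotheses can remain separate claims, each at one-sided 0.05.

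This costs one sentence and a short cross-reference. N=21 is unchanged, no data are added, and 3 mm is still measured and reported. The small loss is that a favourable 3 mm result alone can no longer support the primary claim. The change should be made before the results are seen.

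If the sponsor wants both diameters to count, the plan must say so and be sized for it. An either-diameter rule with alpha halved to 0.025 needs 27 pairs on the same inputs (power 0.692 at 21). A both-must-pass rule needs 3 mm inputs, which the plan does not have.

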The study is a monocular (OD only), subject masked, 2 x 2 randomized, crossover (with an additional non-randomized baseline reference (3 arms in all)) comparing the difference in diurnal change in optical quality with different soft lenses relative to baseline (no lens).

Lens wearing protocol:

1. Subjects will first have measurements acquired every 2 ± 0.5 hours for 12 ± 1 hours without any lenses (no lens, baseline). The subject will wear their habitual spectacles between measurement periods.
2. Following a day of washout with spectacle wear only, each type of lens will be used in both eyes for a period of 2 ± 1 days. Early the following morning, the subject will present to the clinic wearing spectacles. A lens of the same type they have been wearing for the previous few days will be inserted while a masked examiner then performs measurements every 2 ± 0.5 hours for 12 ± 1 hours.
3. Subjects will then be dispensed the next randomized lens pair and told to not wear the lens that day or the following (washout) day, but the next two days. As previous, the subject will present to the clinic on the third day not wearing the lenses. Lenses will be inserted, and then measures will be taken throughout the day.

Measurement protocol:

1. At the beginning of each testing day, aberrometry, Medmont topography (non-invasive tear break-up), and subjective quality measures of the subject's OD eye alone will be captured. This will serve as 'baseline' for each day.
2. The study lenses will then be inserted according to the randomization schedule.
3. Following 10-20 minutes of lens settling, eye+lens aberrometry (minimum 5 mm analysis diameter, Medmont corneal topography, and subjective (0-100 scale) measures will be acquired on the OD. Measures of contact lens position (through recorded imaging) will also be performed. Measures at this time point will serve as "time 0" for each lens wearing day.
4. This cycle will be repeated every 2 ± 0.5 hours up to 12 ± 1 hours.
5. At the end of 12 ± 1 hours, the subject will return all lenses of that set, and be given the next set of lenses to repeat the washout, wearing and measurement cycle.

Dilation Protocol:

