Our within-subject variability and correlation estimates were taken from Cheng, *et al* (2004) who reported on the stability of clinical monochromatic aberrometry measurements over a wide range of time scales. First, temporal variability of wavefront root mean square (RMS) error, excluding defocus and astigmatism, was tracked across five repeated measurements for 4 subjects at four different time scales. The averaged variance estimates for different time scales ranged from $8.10 \times 10^{-5} \mu\text{m}^2$ ($t < 1$ second) to $9.73 \times 10^{-4} \mu\text{m}^2$ ($t < 1$ year). For our calculations, we used their reported value of $4.41 \times 10^{-4} \mu\text{m}^2$ ($t < 1$ week) as our variance estimate, which translates to a standard deviation of 2.1%. We expect that this is a worst-case scenario because the value was derived by calculating the between-day variances for individual trials across five days for each subject and then calculating the average across the four subjects and five trials on each day. Our data will be multiple measurements taken within a 12-hr period on the same day. Second, Cheng, *et al* (2004) reported a within-subject correlation estimate of $r=0.799$ that was based on a linear regression analysis of the higher-order RMS error measurements over a one-year time scale for subject AB. Again, because the time-scale in the current study proposal is only 12 hours (i.e., is much shorter than 1 year), we expect that the magnitude of the within-subject correlation in our sample is likely to be 0.80 higher. For purposes of the sample size calculation, we used three values for the correlation parameter, i.e., $r = \{0.70, 0.75, \text{ and } 0.80\}$. The input parameters for this sample size calculation scenario are shown in Table 1(a). The actual power and number of paired observations for this scenario are presented in Table 1(b) and were obtained using SAS 9.4 by varying both the mean difference and the correlation parameters.

Table 1 (a)

Fixed Scenario	
Distribution	Normal
Method	Exact
Number of Null	L
Alpha	3.50 %
Standard	0.05
Nominal	2.10 %
	0.80

Table 1 (b)

Index	Mean Diff	Corr	Actual Power	N Pairs
1	2.00	0.70	0.810	9
2		0.75	0.822	8
3		0.80	0.838	7
4	2.25	0.70	0.802	12
5		0.75	0.829	11
6		0.80	0.824	9
7	2.50	0.70	0.804	18
8		0.75	0.822	16
9		0.80	0.819	13
10	2.75	0.70	0.806	31
11		0.75	0.805	26
12		0.80	0.803	21
13	3.00	0.70	0.801	67
14		0.75	0.801	56
15		0.80	0.808	46

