1. At the beginning of each measurement day, aberrometry, Medmont topography, and subjective quality measures of the subject's eyes alone (COAS and Medmont) will be captured. This will serve as 'baseline' for each day (for the spectacle day, this will also be "time 0").
2. The study lenses (or no lens for spectacle day) will then be inserted according to the randomization schedule.

3. Following 10-20 minutes of lens settling, the eye+lens aberrometry (minimum 5 mm analysis), Medmont topography, and subjective quality (0-100 scale) measures will be acquired for each eye. This will serve as “time 0” for each lens wearing day.
4. This cycle will be repeated every 2 ± 0.5 hours up to 12 ± 1 hours.
5. At the end of 12 hours, the subject will return all lenses of that set, and be given the next set with a schedule of washout and wear days.

Testing Day 4, Visit 7 = Exit:

1. Exit ocular health (with conjunctival and corneal staining)
2. Exit Snellen visual acuity

STATISTICAL ANALYSIS

[figure not shown]
Separate tables with descriptive statistics will be provided for all baseline, outcome/endpoint and safety variables, as appropriate. Continuous variables will be summarized with location and dispersion parameter estimates while categorical data will be summarized using frequency counts, percentages and margin tables where appropriate. Visualizations and related graphs will be provided in support of these data summaries.

Statistical analyses will be performed only after all data have been collected, transcribed into the electronic database, and error checked and corrected if needed. We will first test for a differential carryover effect of lens using a linear (ANOVA) model. For a crossover design, the model can be expressed as

$$y_{ijkl} = \mu + \alpha_i + \rho_{j(i)} + \gamma_k + \tau_l + \lambda_m + \gamma\tau_{kl} + e_{ijkl}$$

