Second, a comparison of the statistic $\% \Delta_{i(12-0)_{test}}$ for one test lens with $\% \Delta_{i(12-0)_{k-1}}$ the other test lens in the study will be performed by fitting a linear mixed effects regression model with restricted maximum likelihood (REML) estimation. The effect of lens will be parameterized in this model with (0,1) GLM dummy coding using Air Optix with Hydraglide as the reference lens; thus, a separate parameter estimate will be obtained for the other test lens. The initial model will include a single random effect for subject. We will also perform sensitivity analyses by adding covariates and refitting the model with ML to obtain ‘adjusted’ parameter estimates for the fixed effect of lens to account for potential confounding due to measured covariates.

PUBLICATION PLAN:

Work will be presented at least one international meeting, such as American Academy of Optometry, Global Specialty Lens Symposium, ISCLR, BCLA, American Optometric Association, or ARVO. The work will also be prepared for submission for peer-reviewed or trade publication (e.g. Optometry and Vision Science) at Sponsor’s request and if results merit.

TIMELINE: (estimated)

Contract approval: unknown, estimate 1 month

Human subjects approval: 1 month, concurrent to above

Project setup: 1 month, concurrent to above

Recruitment: 1 month, concurrent to above

Data collection: 2 months

Data analysis: 1 month

Report writing: 1 month¹

Contract for 1 year to account for any delays or necessary subsequent analyses.

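### The lens-versus-no-lens non-inferiority tests hang on a carryover pretest that the stated model cannot run from two periods, and that has no level, data set or fallback; test unconditionally instead

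*Combined protocol and SAP*

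**What the plan says.** The Statistical Analysis section opens the inferential work with "We will first test for a differential carryover effect of lens using a linear (ANOVA) model". The model given there holds sequence, subject within sequence, period, lens, carryover and period-by-lens terms together. The one-sided non-inferiority comparison of each lens with no lens then follows under the condition "Assuming that there is no statistical evidence of a period x lens interaction".

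Two other places give the same comparison without that condition. Outcome Measures, Primary, begins "Our initial analysis will compare the mean" and goes straight to each lens against no lens. The Sample Size section rests on "a dependent sample t-test on a mean difference score under the assumption of no differential carryover effect".

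The last paragraph of Statistical Analysis compares the two lenses with a mixed model coded for lens. It adds "The initial model will include a single random effect for subject" and names neither period nor sequence. Only the two lens periods are randomised; the no-lens day is a non-randomised reference and comes first (Study Design).

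**The concern.** Read together, these passages put a preliminary test in front of the primary analysis. Three things needed to carry it out are missing: the data set (two lens days or all three test days), the significance level (0.05 appears only for sample size), and the action if the pretest is positive. The analyses are run after all data are collected, so each choice would be made with outcomes in hand. The data-set choice alone decides whether the test as written exists.

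Where it can be computed, the question is whether passing it means anything. A low-powered pretest usually passes whether or not carryover is present. It also cannot show which lens is affected, and that is what determines the bias in each lens-versus-no-lens mean.

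A related gap is that the lens-versus-lens model, the one randomised comparison, omits the period and sequence terms that can be fitted there.

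**Working it through.** **Inputs.** From Sample Size and Table 1: SD 2.1, correlation r 0.70–0.80, null difference 3.5, alpha 0.05, N = 21 (the row with mean difference 2.75 and r 0.80). Assumed because the plan gives no figure: 10 and 11 completers per sequence, a two-sided 5% pretest (10% also shown), equal SD and correlation across the three days, and an illustrative differential carryover of 1.5 points.

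**Plan's own figure.** SD of the paired difference = 2.1 × √(2(1 − 0.80)) = 1.328. One-sided paired t-test, N = 21, noncentrality √21 × (2.75 − 3.5)/1.328: power 0.803, matching Table 1(b), index 12. All 15 rows reproduce as one-sided tests.

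**Estimability.** Rank of the cell-mean design:

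| Data and base terms | Base rank | + carryover | + period × lens | + both |
|---|---|---|---|---|
| Two lens periods (4 cells): sequence, period, lens | 4 | 4 | 4 | 4 |
| Two lens periods, sequence left out | 3 | 4 | 4 | 4 |
| Three days (6 cells): sequence, period, lens | 5 | 6 | 6 | 6 |

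The first row is saturated, so nothing is left to test. In the other two rows carryover and interaction are a single contrast. Lens minus no lens is not estimable once period is fitted, because no lens is always first; lens minus lens is.

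**Pretest power for 1.5 points** (noncentral t, 19 df; √(1/10 + 1/11) = 0.437):
- Two periods, sequence dropped: SE = SD × √(2(1 + r)) × 0.437 = 1.692 at r 0.70 and 1.741 at r 0.80. Power is 0.134 and 0.130 at 5%, 0.221 and 0.215 at 10%.
- Three days, contrast y2 + y3 − 2·y1: SE = SD × √(6(1 − r)) × 0.437 = 1.231 and 1.005. Power is 0.212 and 0.294 at 5%, 0.322 and 0.419 at 10%.
- Carryover detectable with 80% power at 5%: about 5.0–5.1 points (two periods) or 3.0–3.6 (three days), against a null difference of 3.5.

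The plan takes a variance of 4.41 × 10⁻⁴ µm², that is 0.021 µm, "which translates to a standard deviation of 2.1" percent without showing the conversion, so other SDs are shown (5% level, r 0.70 and 0.80):

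| SD | Two periods | Three days |
|---|---|---|
| 1.5 | 0.218, 0.209 | 0.367, 0.509 |
| 3.0 | 0.091, 0.088 | 0.128, 0.168 |
| 4.2 | 0.071, 0.069 | 0.089, 0.109 |

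**What passing would show.** A carryover onto one lens affects only the sequence that wears it second, so it shifts that lens-versus-no-lens mean by 1.5 × 10/21 = 0.71 or 1.5 × 11/21 = 0.79. Split +0.75/−0.75 between the lenses, the shifts are 0.36–0.39 in opposite directions. Simulation, 100,000 runs, r 0.80, true difference 2.75:

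| Carryover | Non-inferiority success, affected / other lens | Pretest positive, two periods / three days |
|---|---|---|
| None | 0.80 / 0.80 | – |
| 1.5 onto one lens | 0.02–0.04 / 0.81 | 0.13 / 0.30 |
| +0.75 / −0.75 | 0.30–0.34 / 0.98 | 0.13 / 0.29 |

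The ranges reflect which sequence has 10 and which 11. The pretest responds alike to two very different patterns of bias. In the direction that produces false claims (−1.5 onto one lens, true difference at 3.5), the test rejects in about 76% of trials, and in about 76% of those that pass a two-period pretest.

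**Cost with no carryover.** If a positive pretest means no test, power falls from 0.803 to about 0.803 × 0.95 = 0.76 at a 5% pretest, or 0.803 × 0.90 = 0.72 at 10%. Type I error is about 0.05 either way.

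**Lens-versus-lens model** (r 0.80, 10/11). SE with period fitted = 1.328/2 × 0.437 = 0.290. Without it, and with no period effect, 1.328/√21 = 0.290. Without it, under an illustrative 1-point period effect, √((1.328² + 4 × (10/21)(11/21))/21) = 0.363. The share of any period effect entering the lens estimate is 1/21 = 5%, or 3/21 = 14% at an assumed 9/12.

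**The case against.** The plan introduces its equation as a general crossover model. An analyst could drop sequence, or treat the sequence test as the carryover test, and so obtain a result from two periods. That is true, and the non-estimability claim is limited to two periods with sequence fitted. But the plan does not say to do this, and the resulting test has 13% power.

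The conditional phrase might be only a background assumption, as in Sample Size. The instruction to test carryover first and the reference to statistical evidence make that reading hard to sustain.

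The measured harm is modest: about 4 to 8 points of power and no false-positive inflation when carryover is absent. The collapse in success under carryover comes from the bias, and unconditional testing suffers it equally. Both points stand. The case for removing the pretest is that it costs something and protects against almost nothing.

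Stating the data set, level and fallback would also close the specification gap. It would leave a low-powered condition on the primary test.

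The design safeguards should not be oversold. Taking change from the same day's time 0 cancels a proportional day-to-day shift, not an additive one. The documents also use baseline both for the pre-lens measurement and for time 0. Finally, the carryover size and SD range are assumptions: three-day power runs from 9% to 51% across them at the 5% level.

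**Conclusion.** The concern holds. The two terms on which the primary tests are conditioned are one contrast. It is not estimable from two periods with sequence fitted, and has one degree of freedom if the no-lens day is included. Level, data set and consequence are unstated, and other sections give the same comparison unconditionally.

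For an illustrative 1.5 points at SD 2.1, a 5% pretest has 13% or 21–29% power. It does not exceed 51% anywhere in the SD range shown. Passing it is weak reassurance, and with no carryover it costs about 4 points of primary power (8 at a 10% pretest) if failure means no test. These figures rest on the 10/11 split, equal variances and correlations, and the assumed levels and carryover size; the rank result needs none of them.

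Carryover is better limited by design: "Following a day of washout with spectacle wear only", then 2 ± 1 days in the new lens before measurement. The point should be corrected, but it does not undermine the trial. The omission of period and sequence from the lens-versus-lens model is a smaller matter with an easy remedy.

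**What to change.** 1. Delete the no-evidence condition, and remove the carryover and period-by-lens terms from the primary path.
2. Run both lens-versus-no-lens non-inferiority tests unconditionally, as Outcome Measures already reads.
3. Fit the lens-versus-lens mixed model with fixed sequence, period and lens and random subject, by REML.
4. Report the single carryover contrast descriptively with a 95% confidence interval from a named data set. One choice is the three-day set: the sum of the two lens-day changes minus twice the no-lens-day change, compared between sequences. The expected half-width is ±2.1 to ±2.6 points under the plan's inputs.
5. State in the conclusions that lens versus no lens cannot be adjusted for an order effect shared by both lenses. As a clerical matter, reconcile "The study lenses (or no lens for spectacle day) will then be inserted according to the randomization schedule" in Testing Procedures with the no-lens day being non-randomised and first.

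The cost is SAP wording only. N = 21 (24 enrolled) and power 0.803 do not change. The lens-versus-lens model gives up one or two degrees of freedom, with an SE of 0.290 either way when there is no period effect.
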